5 RESEARCH METHODS

5.1 Study design

This is a multi-center, prospective, observational study of MF-CTCL patients who have newly initiated Valchlor or who are continuing treatment with Valchlor.

Patients will be followed by their physician according to routine clinical practice. With the exception of protocol-required patient-completed questionnaires, there are no specific or mandated clinical assessments to be performed, and patients will not receive experimental intervention or treatment as a consequence of their participation in this study. The study protocol will not mandate any specific schedule of visits. Patients will undergo clinical assessments and receive standard medical care as determined by the patient's physician in a real-world setting.

Patients will be followed prospectively for a maximum of 2 years from the date of signed informed consent until end of study (EOS), which includes withdrawal of consent, loss to follow-up, death, or study completion. Continuation in the study is not contingent on continuation of Valchlor.

The study will end after all enrolled patients have been followed for 2 years, or discontinued from the study for any reason.

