5.7.3 Treatment and assessment patterns

Because relatively little prospectively collected data is available on MF-CTCL treatment patterns, preliminary analysis will make use of patient listings to develop categories of treatment patterns. Categories will be developed without cross-referencing outcomes data to minimize bias (i.e., the focus will be the presence of specific assessments, not the test value associated with the assessment). Treatments individually and in combination will be reported in percentage terms, by visit, stratified by newly initiating patients and continuing patients to identify treatment patterns.

Duration of time from first post-initiation of Valchlor office visit to discontinuation of therapy will be assessed using Kaplan-Meier estimates of freedom from discontinuation. If short-term gaps in therapy are common, sensitivity analyses may be conducted in which these gaps do or do not count as treatment discontinuations, depending on the lengths of the gaps. These analyses will focus only on newly initiated patients.

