### **Exposure Definitions and Measures**

Start of observation is defined as date of enrollment.

End of observation is defined as End Of Study (EOS), which includes, adverse event, patient withdrew consent, patient lost to follow-up, physician's decision to withdraw or study completion, whichever occurs first.

Total exposure time is defined as the date of first Valchlor exposure to the date of last Valchlor exposure.

Total on-study Valchlor exposure time is defined as the first day of Valchlor use to last day of Valchlor use during the observation period. If the patient was using Valchlor at the end of observation, the last on-study day of Valchlor use is equal to the end date of observation period.

Patients may discontinue Valchlor while on study. In this case, the last day of Valchlor exposure will be when the patient discontinues Valchlor (as reported on the Valchlor treatment log). Patients who restart Valchlor after discontinuing will then begin adding Valchlor exposure days once Valchlor is restarted through the end of the study. For the patients that restart Valchlor during the study, the Total on-study Valchlor exposure will be a sum of all days in which Valchlor was dosed during the study, as reported on the Valchlor treatment log.

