## METHODS FOR HANDLING MISSING DATA

Because this is an observational study, data that are not present at a particular assessment will generally reflect clinical practice rather than a data quality issue. As data are not expected to be missing at random, no plan exists to impute missing data or utilize models which

assume data are missing at random. For any results considered for external dissemination (e.g. publication), additional analyses will need to be conducted to compare the patients who did and did not contribute data to the analysis to assess the potential for bias.

Type of Date	Date is incomplete	Date is completely missing
Date of Valchlor start or discontinuation	Valchlor start: If the month and year is present but the date is missing then impute the 15th day of that month. Valchlor discontinuation: If day of Valchlor discontinuation is missing and month and year are present, day is replaced by the 15 th .	Valchlor start: No replacement Valchlor discontinuation: If observation period under Valchlor is stopped due to adverse event or loss to follow-up, but no Valchlor discontinuation date is provided, the Valchlor discontinuation date is respectively the date of adverse event reported on the Termination CRF or last treatment information date available (for lost to follow-up) or withdrew consent or physician decision to withdraw.
Date of start event leading to reason for Valchlor prescription	If year is known then impute 30 th June of that year. If year and month is known then impute 15 th of that month and year. If imputed day (using rules above) is after date of enrollment, then impute enrollment date – 1 day.	No replacement
Date of medication start/stop date	If year is known then impute 30 th June of that year. If year and month is known then impute 15 th of that month and year. If imputed day (using rules above) is before start date of Valchlor, then impute start date of Valchlor + 1 day. Year & month present, day missing: If month and year is the same as data cut then use the data cut. If month and year is before the data cut then use 15 th of that month. Year present, Month missing: If year is the same as the data cut the use the data cut. If the year is before the data cut then use 30 th of June of that year.	No replacement

Statistical Analysis Plan  
Valchlor PROVe  
November 2019  
Version Number: 3.0

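### For a patient lost to follow-up while on Valchlor with no stop date, two SAP rules give different last-use dates, and neither says whether the imputed date counts as discontinuation

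*SAP*

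**What the plan says.** **Missing-date rule (SAP, Methods for Handling Missing Data, row on Valchlor start or discontinuation, completely missing dates).** The condition is "If observation period under Valchlor is stopped due to adverse event or loss to follow-up, but no Valchlor discontinuation date is provided". The SAP then assigns a Valchlor discontinuation date. For an adverse event it is the event date on the Termination CRF. Otherwise it is the "last treatment information date available (for lost to follow-up) or withdrew consent or physician decision to withdraw". The last two reasons appear only at the end of the sentence, not in its condition, so it is unclear which date they receive.

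**Exposure rule (SAP, Exposure Definitions and Measures).** Leaving the study is itself an end of observation: "End of observation is defined as End Of Study (EOS), which includes, adverse event, patient withdrew consent, patient lost to follow-up". The section continues: "If the patient was using Valchlor at the end of observation, the last on-study day of Valchlor use is equal to the end date" of the observation period. Protocol 5.3.2 has the same rule. For a patient who does discontinue on study, the SAP takes the last day from the Valchlor treatment log.

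**Context.** Protocol 5.1 keeps the two kinds of stopping apart: "Continuation in the study is not contingent on continuation of Valchlor". Protocol 5.7.3 says that time to discontinuation in newly initiated patients "will be assessed using Kaplan-Meier estimates of freedom from discontinuation", with no event or censoring rule for patients who leave the study. The protocol's Rationale and the SAP's Introduction both name discontinuation rates among the things the study is meant to clarify.

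**The concern.** The missing-date rule is triggered when observation on Valchlor ends. That most naturally describes a patient who was on the drug when last seen, which is close to the condition of the exposure rule. For loss to follow-up, one rule gives the last date with treatment information and calls it a discontinuation; the other gives the end of observation and calls it the last day of use. Nothing ranks the two.

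The label matters more than the date. Losing contact with a patient does not show that Valchlor was stopped. If a programmer treats every populated discontinuation date as an event, dropouts enter the count of discontinuers. The outputs that could be touched are:

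- the protocol's Kaplan-Meier freedom-from-discontinuation analysis, newly initiated patients only;
- the quarterly VAS and Skindex-29 summaries by Valchlor discontinuation (SAP Statistical Methods, Table 17b);
- the Table 21a comparison subset, which the SAP describes by discontinuation alone.

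Exposure days also depend on which rule is programmed.

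**Working it through.** **1. The rules side by side, for a patient lost while on Valchlor with no logged stop**

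| | Missing-date rule | Exposure rule |
|---|---|---|
| Condition | Observation on Valchlor ended by loss to follow-up, no stop date | Using Valchlor when observation ends |
| Date given | Last date with treatment information | End of observation |
| Label | Discontinuation date | Last on-study day of use |
| Event or censored | Not stated | Not stated |

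For withdrawn consent there are two readings. If the assigned date is the withdrawal date, it equals the end of observation, so the dates agree and only the label differs. If it is the last treatment information date, the conflict is the same as for loss to follow-up.

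**2. The plan's own figures (protocol 5.5).** These reproduce and are not in dispute. 270 evaluable patients with 10% incomplete follow-up: 270 / 0.90 = 300. Margin of error for a subgroup of 100: 1.96 × √(0.25/100) = 9.8 points, against the stated 10. No figure in either document depends on the missing-date rule.

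**3. Illustration of the event-or-censoring choice.** The inputs are borrowed, because the documents give no count of dropouts without a stop date:

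- d, true discontinuation by 12 months: 15-20%. This is the SAP's share who discontinued and switched therapy, not a discontinuation rate.
- w, lost while on Valchlor with no stop date: 10%. This is the protocol's allowance for incomplete follow-up. The range shown is 5% to 20%.

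With loss independent of discontinuation, the 12-month rate is d if losses are censored and 1 − (1 − d)(1 − w) if they are events.

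| w | d = 15% reads as | Excess | d = 20% reads as | Excess |
|---|---|---|---|---|
| 5% | 1 − 0.85 × 0.95 = 19.25% | 4.25 points | 1 − 0.80 × 0.95 = 24.0% | 4.0 points |
| 10% | 1 − 0.85 × 0.90 = 23.5% | 8.5 points | 1 − 0.80 × 0.90 = 28.0% | 8.0 points |
| 20% | 1 − 0.85 × 0.80 = 32.0% | 17.0 points | 1 − 0.80 × 0.80 = 36.0% | 16.0 points |

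The Kaplan-Meier analysis covers newly initiated patients only, so the subgroup planning size of 100 is the relevant base. The simple binomial standard errors are √(0.15 × 0.85/100) = 3.57 points and √(0.20 × 0.80/100) = 4.0 points. At w = 10% the excess is 8.5/3.57 = 2.4 and 8.0/4.0 = 2.0 standard errors.

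**4. Exposure days.** Take 30 such dropouts (10% of 300) and an assumed gap of 30, 90 or 180 days between last treatment information and end of observation. The rules then differ by 900, 2,700 or 5,400 person-days. Against 300 × 365 = 109,500 days that is 0.8%, 2.5% or 4.9%; against 300 × 730 = 219,000 it is 0.4%, 1.2% or 2.5%.

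**5. The 12-month response analyses.** The SAP's exclusion from the primary analysis describes permanent discontinuation together with a switch to new therapy. An imputed stop date alone does not meet that. The window is 365 ± 90, or days 275 to 455, so a patient lost before day 275 has no BSA value in it under either rule. The Table 21a subset is exposed only through patients who have a value in the window and also carry an imputed stop date.

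**The case against.** The strongest reply is that the missing-date table only supplies dates. It never says that an imputed date is a discontinuation event, and the exposure section ties discontinuation to the treatment log. A reader might infer that dropouts are therefore counted as discontinuers and that reported rates will be inflated. The documents do not go that far: if imputed dates only censor, the rate is unaffected. That stands, and it limits the point to what can happen under a literal reading.

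The exposure rule is also conditional. It does not declare every dropout to be on drug, and it says nothing about censoring. After three failed contact attempts (protocol 5.9), current use may simply be unknown, and the missing-date rule can be read as filling that gap. Protocol 5.8 lists Valchlor interruption and discontinuation among the items to be queried, so blank stop dates should be chased. Both points stand in part. They may make the overlap rarer, but they do not say which rule applies when it occurs.

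The affected outputs are fewer than a reader might assume. The Kaplan-Meier analysis is in the protocol; the SAP has no text or shell for it. Scaling the excess against all 270 evaluable patients would use the wrong population. Table 17b's shell title includes early termination, so early leavers may be in it by design. Table 5 is a weak example, because the SAP's table list calls it prior treatments although its shell title refers to discontinued therapies.

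**Conclusion.** The conflict is real and narrow. For a patient on Valchlor when lost to follow-up with no recorded stop, the SAP has two rules that can differ on date and on label, with no order of precedence and no statement of whether the imputed date is an event. The wording for withdrawn consent and physician decision also needs repair.

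The possible effect on a discontinuation rate is 8.0 to 8.5 points at 10% lost on drug and about 4 points at 5%. These figures rest on borrowed inputs, loss independent of discontinuation, and imputed dates being counted as events. They show what the ambiguity could cost; they do not estimate a bias in reported results. The effect on exposure days is small under the gaps assumed. The documents do not show that the primary 12-month exclusion is affected. The point merits correction because discontinuation rates are a stated interest of the study and the remedy is short.

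**What to change.** Use one last-use date for these patients in both SAP sections, for example the last date with treatment information. The missing-date rule already uses that date for loss to follow-up, so the date that would change is the one in the exposure definitions. Note the resulting difference from protocol 5.3.2.

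Then add wording to this effect: where no stop date is recorded and the patient leaves the study, the imputed date ends exposure and censors the patient in any discontinuation analysis. It does not classify the patient as a discontinuer unless the Valchlor Treatment Log or Termination CRF records that Valchlor itself was stopped. State separately which date applies to withdrawn consent and to physician decision.

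The cost is a short change of SAP text and one programming rule. If imputed dates would otherwise have been counted as events, the reported discontinuation rate will be slightly lower and the discontinuation groups smaller.

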**Table 1 eCRF Data Collection**

Variables	Enrollment visit	Post-enrollment follow-up visits
Demographics		
Age, gender, race/ethnicity, height	X	
Weight*	X	
Relevant Medical History		
Age at diagnosis of MF-CTCL	X	
Date of MF-CTCL diagnosis	X	
Method of diagnosis	X	
MF-CTCL TNMB classification*	X	
MF-CTCL TNMB classification change		X
MF-CTCL histology	X	
Malignancies and secondary malignancies	X	
Non-melanoma skin cancers	X	
Prior viral infections	X	
Atopic disorders	X	
Psoriasis	X	
Urticaria	X	
Mental disorders	X	
Family medical history	X	
Other relevant medical history	X	
Changes in medical history		X
Targeted MF-CTCL Treatments (Medication Use and Dosing)*		
Valchlor	X	X
Other MF-CTCL treatments	X	X

Variables	Enrollment visit	Post-enrollment follow-up visits
Healthcare utilization related to MF-CTCL (as assessed by physician)		
Hospital admissions ‡		X
Emergency room visits		X
Clinical Status (as assessed by physician)	X	X
Clinical Status Assessments*		
Composite Assessment of Index Lesion Severity	X	X
Modified Severity Weighted Assessment Tool	X	X
Physician's Global Assessment	X	X
Body Surface Area of disease	X	X
Patient-Completed Questionnaires§		
Visual Analogue Scale for pruritus	X	X
Skindex-29	X	X
Safety Measures**		
AEs and SAEs	X*	X
Reports of secondary exposures		X †

\*Included in pre-treatment data collection, which is performed at enrollment. All data must be completed as available.

†Includes collection of start and stop dates for each medication, including reasons for starting and stopping medications. Start and stop dates are also collected for Valchlor, including short gaps in treatment, such as drug holidays.

‡For each hospital admission, length of stay and primary admission and discharge diagnoses will be collected.

§To be completed by patients who can read and understand English and are able to self-complete the questionnaires based on the investigator's assessment. Patients who are unable to self-complete the questionnaires will not be excluded from the study.

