### **Other MF-CTCL Treatments**

Other MF-CTCL medications will be categorized by specific therapies (skin-directed therapies, systemic therapies and other) and identified by comparing the start/stop dates of the various medications/therapies recorded on the Other MF-CTCL Treatments Log with the date of enrollment from the Enrollment eCRF. A table summarizing pre-treatments and therapies that were stopped prior to enrollment will be included, as well.

Patients will be considered to be on other medications/therapies (specific for MF-CTCL). The data will include the medication/therapy start date either on the day of enrollment or before the day of enrollment and have either continued or stopped taking the medication after the day of enrollment. By this algorithm, patients who start a medication on the day of enrollment will be considered to be on that medication at enrollment, patients who start and stop a medication on the day of enrollment will be considered to be on that medication at enrollment, but patients who stop a medication on the day of enrollment will not.

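### The SAP's partial-date rule for medications does not separate starts from stops, and one of its two rule sets moves dates known to precede Valchlor to the day after Valchlor start

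*SAP*

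**What the plan says.** The table in the SAP section on handling missing data has one row for medication start and stop dates. Its cell for incomplete dates holds two sets of rules.

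- **Set 1.** Year only: 30 June. Year and month: the 15th. Then the override: "If imputed day (using rules above) is before start date of Valchlor, then impute start date of Valchlor + 1 day".
- **Set 2.** Arranged by what is missing, not by start or stop. Day missing: "If month and year is the same as data cut then use the data cut", otherwise the 15th. Month missing: the data cut if the year is the same, and "If the year is before the data cut then use" 30 June. There is no Valchlor override.

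The Valchlor row of the same table does label its parts. It begins "Valchlor start: If the month and year is present but the date is missing then impute the 15th day of that month" and then gives a separately labelled rule for discontinuation.

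Past therapies are within reach of the row. A footnote to SAP Table 1 says of the treatment data: "Includes collection of start and stop dates for each medication, including reasons for starting and stopping medications". Another says: "Included in pre-treatment data collection, which is performed at enrollment. All data must be completed as available". The section on other MF-CTCL treatments says that other therapies are "identified by comparing the start/stop dates of the various medications/therapies recorded on the Other MF-CTCL Treatments Log with the date of enrollment", and adds: "A table summarizing pre-treatments and therapies that were stopped prior to enrollment will be included, as well". The Table 28 shell has separate columns for therapies used before and during mechlorethamine treatment.

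**The concern.** Two programmers could follow this cell faithfully and derive different dates. More seriously, set 1 overrides what the site recorded. If the recorded year or month lies wholly before Valchlor start, the true date cannot be the day after Valchlor start, yet that is the date the rule assigns.

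What is at stake is the line between prior and concomitant therapy. Dates for past treatment are collected only as far as they are available, so partial dates are most plausible for the therapies on which the override acts.

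**Working it through.** **Inputs.** The two rule sets are taken literally from the SAP cell. The documents give no individual Valchlor start date and no data-cut date, so the dates below are assumptions for illustration: a past therapy from 10 Mar 2010 to 20 Sep 2011, Valchlor start on 1 Dec 2014, and partial meaning year only. The SAP states no figure to reproduce.

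**Where the sets agree.** For periods after Valchlor start and before the data-cut period they match: 2017 gives 30 Jun 2017 and May 2017 gives 15 May 2017 under both. They part when the imputed day falls before Valchlor start, or when the date lies in the data-cut month or year.

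**Finished past therapy.** Set 1 turns both 2010 and 2011 into 1 Dec 2014 + 1 day = 2 Dec 2014. Set 2 gives 30 Jun 2010 and 30 Jun 2011.

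| Set for start / set for stop | Exact start, partial stop | Partial start, exact stop | Both partial |
|---|---|---|---|
| 1 / 1 | 10 Mar 2010 to 2 Dec 2014: false overlap | 2 Dec 2014 to 20 Sep 2011: −1,169 days | 2 Dec 2014 to 2 Dec 2014: one-day course on Valchlor |
| 1 / 2 | 10 Mar 2010 to 30 Jun 2011: valid | 2 Dec 2014 to 20 Sep 2011: −1,169 days | 2 Dec 2014 to 30 Jun 2011: −1,251 days |
| 2 / 1 | 10 Mar 2010 to 2 Dec 2014: false overlap | 30 Jun 2010 to 20 Sep 2011: valid | 30 Jun 2010 to 2 Dec 2014: false overlap |
| 2 / 2 | 10 Mar 2010 to 30 Jun 2011: valid | 30 Jun 2010 to 20 Sep 2011: valid | 30 Jun 2010 to 30 Jun 2011: valid |

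Arithmetic: 20 Sep 2011 to 20 Sep 2014 is 1,096 days, and 73 more reach 2 Dec 2014, so 1,169. From 30 Jun 2011 it is 1,096 + 155 = 1,251.

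**Therapy continued on Valchlor.** Start recorded as 2010, stop on 10 Mar 2016. With set 1 for starts the course runs from 2 Dec 2014 (464 days) and its prior use disappears. With set 2 it runs from 30 Jun 2010 (2,080 days).

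**Limits of set 2.** It avoids these errors but is not safe everywhere. An exact start of 10 Nov 2010 with a stop recorded as 2010 gives a stop on 30 Jun 2010, 133 days before the start. If Valchlor began on 1 May 2014, a therapy stopped in March but recorded as 2014 gets a stop on 30 Jun 2014, which is a false overlap. Dates within one year or month can be misordered or overlap under either set.

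**Data-cut period.** The SAP is dated November 2019. If the cut fell between 1 July and 30 November 2019, a date recorded as 2019 differs between the sets by 1 to 153 days. With a 2020 cut, the sets agree for 2019.

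**Pool of patients.** From the counts printed in Table 28, those who used a therapy before but not during Valchlor number at least 226 − 125 = 101 of 289 (35%) for skin-directed therapy and 83 − 47 = 36 of 289 (12%) for systemic therapy. Only patients with partial dates could be affected, and the SAP does not say whether these counts already reflect the imputation.

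**The case against.** The strongest defence is that the labels were merely dropped: set 1 was meant for starts and set 2, with its data-cut rule, for stops. That is plausible but not stated, and it does not rescue the override. In the 1 / 2 line of the table, a partial start still falls after its own stop. Another reading is that set 2 only refines set 1 near the data cut. The sets then no longer compete, but the override still applies to dates known to precede Valchlor. Nor does the text confine the row to concomitant drugs.

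The objections to the consequences largely stand.

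- The one stated use of log dates compares them with enrollment. That classification changes only if Valchlor began on the day of enrollment or the day before.
- The Table 1C shell counts patients who reach set durations and does not say that past courses are included. The duration column of Table 28 covers the study period only. The source of its prior column is not given.
- Protocol section 5.8 provides for review and possible querying of incomplete data, so partial dates during the study may be few.

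A reader might infer that past users are falsely drawn into the corticosteroid group and so into the primary endpoint. That would need set 1 to govern stops, or membership to be judged on start date alone, and the SAP states neither. A reader might also infer that a moved start counts as an add-on treatment one day into Valchlor. That depends on a time origin for time to next treatment that the SAP does not give. Finally, the failing cells in the table are not a failure rate: they come from one chosen therapy and give equal weight to four readings.

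**Conclusion.** The rule is wrong as written and should be fixed. The cell does not assign its two rule sets to starts and stops, and the override in set 1 gives false dates whenever the recorded year or month lies wholly before Valchlor start. This holds on the start-then-stop reading too. It follows from the text alone; the illustrative dates affect only the size of the gaps.

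The consequences are conditional. Where log dates feed the prior and during columns of Table 28, a therapy can be put in the wrong column. Effects on group membership, time to next treatment and Table 1C cannot be established from the documents. With the number of partial dates and the data-cut date unknown, no effect on any endpoint is claimed. The figures of at least 101 and 36 of 289 describe a pool of prior-only users, not affected patients.

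**What to change.** Replace the cell with the following.

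1. **Separate, labelled rules for starts and stops.** Use the 15th or 30 June, no later than the data cut. For a stop in the same period as the cut, use the data cut.
2. **No contradiction of recorded data.** Never move a date whose known year, or month and year, lies wholly before Valchlor start. Apply no Valchlor floor to stop dates.
3. **Ambiguous starts.** If the known period contains the Valchlor start, keep the 15th or 30 June, or state the floor as an explicit convention that never places a start after its stop. Flag these records and report prior and during counts both ways, because a floor here can still erase the prior use of a continuing therapy.
4. **Check.** Query any record whose start falls after its stop. This also catches the same-period misorderings that no midpoint rule avoids.
5. **Outputs.** Re-derive Table 28 and any other output that uses these dates, and report the number of imputed dates.

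The cost is one rewritten table cell, a small amount of reprogramming, and a re-run of the tables that use these dates.
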